6.3. WITHDRAWAL AND /EARLY DISCONTINUATION CRITERIA

In addition to screening failure, the reasons for a patient's premature withdrawal or early discontinuation from the study may be the following:

- The patient's or legal representative's decision that can occur for any reason and at any time

- The Investigator's decision in the patient's interest. Particularly, if a serious adverse event occurs and is considered by the Investigator liable to threaten the health of the patient
- An erroneous inclusion according to the protocol. The decision to maintain the patient or not in the study will be taken jointly by the Investigator and the Promoter
- Promoter's or Competent Authorities' motivated decision
- Other reasons, to be specified, such as: death, adverse events, lack of efficacy, major protocol violation, non-compliance, pregnancy, loss at follow-up.

The Investigator should attempt to collect, as soon as possible, the following information for a final assessment:

- reason(s) for withdrawal to be reported in the case report form
- evaluation of the patient's clinical condition
- if necessary, take appropriate therapeutic measures: management of an adverse effect or concomitant disease, prescription of another treatment
- recover the investigational product previously given to the patient.

In all cases, available data will be kept for the safety analysis.

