5.2. DISCUSSION OF THE STUDY DESIGN

5.2.1. Choice of the Study Population

A total of 25 patients with non-valvular atrial fibrillation, high atrial fibrillation-related stroke risk, and documented LA or LAA thrombosis will be included in the study.

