11.2.4. SAE Occurring After the Study

Because of the 4 week follow-up after the end of treatment, any SAE occurring after the end of the study last follow-up visit will not be notified to the Promoter.

However, the Promoter must be notified of any event occurring at any time after the end of the study (last follow-up visit) for the patient who may be related to the study treatment in the Investigator's opinion.

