14.2. SAMPLE SIZE

There are no previous studies conducted with edoxaban on atrial thrombus dissolution, and this is a pilot trial. For this reason, the sample size has beeen determined empirically, on the basis of case reports with similar products in this clinical conditions (6, 8-10, 15).

However, if the proportion of patients with thrombus dissolution after 4 weeks of treatment will be 60%, which is compatible with the above-mentioned case reports, a sample size of 25 produces a two-sided 95% confidence interval with range 39-79%.

The involvement of 6-8 sites implies an enrolment of an average of about 4 patient per site to be recruited in about 15 months.

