14.4. DATA SETS ANALYSIS

The following data sets will be analyzed:

- The Full Analysis Set (FAS), composed of all patients having received at least one dose of the study treatment. This data set will be used to perform analyses of Safety and Efficacy.
- The Per Protocol (PP) set, which is the subset of the Full Analysis Set composed of all patients without any major protocol deviation or other source of bias for primary criteria analyses and characterised by a treatment compliance $\geq 80\%$.

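### Section 6.3 does not separate stopping edoxaban from leaving the study, so patients who stop early need not be systematically followed for bleeding, embolism or the week-4 TEE

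*Protocol*

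**What the plan says.** - **Exit route.** Protocol section 6.3 states that, besides screening failure, "the reasons for a patient's premature withdrawal or early discontinuation from the study may be the following". Its last item reads "Other reasons, to be specified, such as: death, adverse events, lack of efficacy, major protocol violation, non-compliance, pregnancy, loss at follow-up". An SAE that the investigator thinks threatens the patient is also listed. Erroneous inclusion is listed too, but whether to keep that patient is a joint decision.
- **Exit assessment.** The investigator is to try to obtain the reason for leaving, the patient's clinical condition, any therapeutic measures needed, and the unused product. Section 6.3 then says "In all cases, available data will be kept for the safety analysis".
- **Scheduled assessments.** The flow-chart places the follow-up visit at week 4 and the telephone assessment at week 8, each ± 3 days. Both include bleeding and thromboembolic events; week 4 also includes the TEE. Section 10.2 describes the week-4 visit as following four weeks of treatment.
- **Denominator.** Section 14.4 defines the FAS as "composed of all patients having received at least one dose of the study treatment", and section 14.8 uses it for all safety criteria.
- **Follow-up after treatment.** Section 11.2.4 justifies not notifying later SAEs with the words "Because of the 4 week follow-up after the end of treatment". It then excepts events that the investigator thinks may be related to treatment.
- **Early stops in the analysis.** Section 14.5.1 counts patients who stopped the drug early, describes them by their time to withdrawal, and rules out replacing missing data.

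**The concern.** Adverse events, lack of efficacy and non-compliance are usually reasons to stop a drug. They do not mean that the patient refuses to be followed. Section 6.3 places them under exit from the study, and section 14.5.1 mixes the two ideas by measuring drug stoppers by time to withdrawal. A site that follows 6.3 literally can close out such a patient after one contact.

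Bleeding and stroke or peripheral embolism are the named secondary objectives (section 3.2), and complete resolution on TEE is the primary one. All patients enter with atrial thrombus and a CHA₂DS₂-VASc score above 1, so what happens after an anticoagulant is stopped matters. With every dosed patient in the denominator, an event that nobody asks about can only lower the reported incidence. The results are also meant to inform a larger comparison with warfarin.

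This is a question of what sites are told to collect. An analysis plan cannot recover outcomes that were never sought.

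**Working it through.** **1. The plan's own figure.** Section 5.2.1 plans "A total of 25 patients with non-valvular atrial fibrillation". Section 14.2 says that, "if the proportion of patients with thrombus dissolution after 4 weeks of treatment will be 60"%, then "a sample size of 25 produces a two-sided 95% confidence interval with range 39-79"%. The exact (Clopper-Pearson) interval for 15/25 is 38.7% to 78.9%, so the figure reproduces. It assumes that all 25 patients are evaluable. The concern does not depend on it.

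**2. What an early stopper is guaranteed.**

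| Outcome | Scheduled for | Required at a 6.3 exit? | Other route |
|---|---|---|---|
| Bleeding, embolism up to exit | week 4 | no specific enquiry | captured as AE or SAE (9.2.1, 9.2.3, 9.2.4) |
| Course of a recorded SAE | – | – | followed to resolution or stabilisation (11.2.3) |
| New bleeding or embolism after exit | weeks 4 and 8 | no | notified only if thought possibly related (11.2.4) |
| Thrombus status on TEE | week 4 | no | none |

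The last two rows are the gap.

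**3. Which safety percentages can move.** The percentages are taken here per patient. A patient who stops because of a bleed already counts in the overall bleeding percentage, so a second bleed does not change it. An unseen embolism, a first bleed, or a later bleed in a more severe category can change the relevant figure. Where it does, each patient is 1/25 = 4 percentage points.

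**4. Illustrative size.** The protocol gives no early-stop rate. Assume d = 1 to 5 stoppers without later observation, none already counted for the event in question.

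- With one event observed elsewhere, the reported rate is 1/25 = 4.0% (exact 95% CI 0.1–20.4%). If every stopper had an unseen event, the rate would be (1 + d)/25: 2/25 = 8% for d = 1, up to 6/25 = 24% for d = 5 (CI 9.4–45.1%).
- With no events observed, the exact upper 95% limit is 1 − 0.025^(1/n): 13.7% for n = 25, 14.2% for n = 24 and 16.8% for n = 20, if only fully observed patients count.
- For the primary endpoint, take 15 observed resolutions. If the stoppers lack a week-4 TEE, the rate among all 25 lies between 15/25 = 60% and (15 + d)/25, which is 64% for d = 1 and 80% for d = 5. If they leave the denominator instead, it becomes 15/24 = 62.5% to 15/20 = 75%.

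**5. Does the existing call come late enough?** Week 8 is day 56. For a stop on day 10, 56 − 10 = 46 days after the last dose. On the nominal day, anyone stopping before day 28 is called more than 28 days later. At the earliest permitted day, 56 − 3 = 53, this still gives at least 28 days for stops up to day 25 (53 − 25 = 28). No specially timed call is needed.

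**The case against.** A reader might infer that the protocol sends every patient who stops edoxaban out of the study and leaves that patient unobserved. The text does not support this.

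- Section 6.3 says only that the listed reasons may lead to withdrawal. Nowhere does the protocol say that stopping the drug ends participation or forbid further follow-up.
- Sections 9.3 and 14.9 have a compliance category for fewer than 21 tablets, and 9.3 has tablets counted at the follow-up visit. Some patients who took much less than the full course are thus expected at week 4.
- The flow-chart times its visits from day 0 without an exception for patients off drug.
- The event that causes the stop is recorded, the clinical-condition item can pick up a bleed or embolism present at exit, and the SAE routes in step 2 continue.

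A reader might also infer that every unseen event costs 4 points. As step 3 shows, a repeat bleed in a patient already counted does not change the overall bleeding percentage. It can further be said that this is a small descriptive pilot, and that no early-stop rate supports any particular size of bias.

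All of this stands, and it limits the point. It does not remove it. The compliance category shows that some under-dosed patients are expected at week 4. It does not say that a patient taken out under 6.3 is among them. The remaining routes are passive or depend on a judgement of relatedness, and none asks every stopper about new bleeding or embolism. With 6–8 sites, silence on this invites different practice from site to site.

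**Conclusion.** The point holds in a limited form. Section 6.3 has one exit route covering reasons that concern only the drug, and its exit assessment secures neither the week-4 TEE nor later enquiry about bleeding and embolism. Sections 14.4, 14.8 and 11.2.4 nevertheless rely on such follow-up for all dosed patients. After exit these patients are not systematically observed; they are not wholly lost to view.

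Any error in the safety rates is downward. It concerns later embolism and first or more severe later bleeds, at 4 percentage points per affected patient. The primary outcome loses one TEE result per such patient. The total size cannot be derived: the 1 to 5 stoppers used above are an assumption, and the effect arises only if sites apply 6.3 literally. The gap should be closed by amendment, but it does not undermine the design.

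**What to change.** Amend section 6.3 to distinguish two situations:

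- **(a) Stopping study drug.** State that the patient stays in the study and completes the scheduled week-4 visit, including the TEE where the patient agrees, and the scheduled week-8 telephone assessment of bleeding and thromboembolic events.
- **(b) Withdrawal of consent, loss to follow-up or death.** Add bleeding and thromboembolic events up to exit to the final-assessment list.

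Section 14.5.1 should then use the same two terms. The change sets no rule on when treatment is stopped or what replaces it, and it uses contacts already in the schedule. The cost is one amendment and a little extra site effort for a few patients. Some of them will decline the TEE, so part of the primary-outcome gap will remain.

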7. STUDY TREATMENT

All patients will receive edoxaban 60 mg once a day, with an open-label design, for 4 weeks. Edoxaban daily dose will be reduced to 30 mg/day in case of: body weight \leq 60 kg, or concomitant therapy with verapamil/quinidine/dronedarone.

7.1. PACKAGING AND LABELLING

The treatment units will be the commercial product manufactured by Daiichi Sankyo. It is dispensed in form of film-coated tablets and packed in blisters.

The commercial outer boxes will be labelled according to European Directives and local requirements.

At the baseline visit, the Investigator will provide the patients with the medications necessary to complete treatment until the next follow-up visit.

7.2. DRUG ADMINISTRATION

One tablet daily to be taken as a whole with some water, with or without food, for a period of 28 days.

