2.5. OVERALL RISK AND BENEFIT ASSESSMENT

Anticoagulant therapy is anyway necessary for the population under study

Patients with AF have an increased risk of recurrent embolism, and therefore should receive anticoagulant therapy. In particular, for patients with CHA₂DS₂-VASc score >1 the Guidelines for the management of atrial fibrillation (1) recommend an anticoagulant therapy in any case. Either oral anticoagulant therapy (OAC), including non-vitamin K oral anticoagulants (NOACs), or aspirin 75–325 mg daily are recommended, with preference of OAC to aspirin.

No use of placebo

Placebo is not used in this study, neither as a comparative agent nor as an add-on agent, in the cohort of patients under study.

Edoxaban is safer than warfarin

In the pivotal ENGAGE AF-TIMI 48 study (7) it has been demonstrated that more than half of the lower rates of all-cause deaths with edoxaban as compared to warfarin were directly attributable to fewer fatal bleeding events and non-fatal major bleeding that contributed to a death within 30 days. There were no differences between edoxaban and warfarin in deaths due to non-cardiovascular causes, nor for any of the 3 most common cardiovascular causes of death, sudden cardiac death, heart failure, ischemic stroke. However, warfarin was associated with approximately twice the risk of fatal bleeding as compared to edoxaban

Positive results with other NOACs

There have been few recent case reports about the resolution of LAA thrombus in patients treated with NOACs (6, 8-10), showing disappearance of thrombi after very 5 weeks or less of NOACs treatment, and consistently suggesting that such therapy might be effective the this clinical condition.

Summary of risk and benefit assessment

Taking into account all medical needs, the positive safety data of edoxaban compared to warfarin, and the encouraging efficacy data from drugs belonging to the same class, it can be reasonably concluded that the participation to this study does not expose the patient to unforeseen risks.

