9.3. COMPLIANCE

The patient will be reminded to bring back, at each visits, any remaining tablets, boxes (used or unused). At the follow-up visit, the Investigator will record the number of supplied and remaining tablet in the CRF.

Considering the duration of the study, compliance will be judged as:

- Complete if $\geq 100\%$ taken (28 tablets or more)
- Adequate if $\geq 75\%$ and $< 100\%$ taken (at least 21 tablets)
- Non adequate if $< 75\%$ taken (less than 21 tablets).

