14.7. EFFICACY ANALYSIS

14.7.1. Primary Criterion

The primary outcome will be the detection of the percentage of patients, after 4 weeks of edoxaban treatment, with complete thrombus resolution by TEE, evaluated with the following probe angulations: 0°, 45°-to-60°, 90°.

As this is a single arm, open-label study, in principle, only a descriptive statistical analysis will be performed for the primary criterion. The primary analysis will be performed both on the FAS and the PP sets. Whenever appropriate, the statistical significance level will be 5%.

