14.9. COMPLIANCE

Compliance will be judged as:

- Complete if \geq 100% tablets taken (28, or more)
- Adequate if \geq 75% and $<100\%$ tablets taken (at least 21)
- Inadequate if $<$ 75% tablets taken (less than 21).

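### Dosing fixed at 28 days and compliance classes fixed at 28 and 21 tablets do not fit a week-4 visit that may fall on days 25 to 31

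*Protocol*

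**What the plan says.** The flow-chart in the protocol synopsis puts baseline and drug dispensation on day 0. It puts the only on-treatment visit at week 4 with a tolerance of three days, and the second TEE and the compliance check both belong to that visit.

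- **Duration.** Section 7 gives 4 weeks of treatment. Section 7.2 gives one tablet daily "for a period of 28 days".
- **Supply.** Section 7.1 has the investigator hand out "the medications necessary to complete treatment until the next follow-up visit", with no number of tablets.
- **Compliance classes.** Under 9.3 the tablet count is recorded at the follow-up visit. The top class is 100% or more "taken (28 tablets or more"), the middle class is from 75% to below 100% "taken (at least 21 tablets"), and fewer than 21 tablets is the bottom class. Section 14.9 repeats this: "tablets taken (28, or more"), then 21.
- **Per Protocol set.** Section 14.4 requires patients to be "characterised by a treatment compliance" of at least 80%, and does not say 80% of what.
- **Clinical setting.** Section 2.5 states: "Anticoagulant therapy is anyway necessary for the population under study".

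**The concern.** Three rules are written for a visit on exactly day 28, while the protocol permits seven different visit days.

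For a late visit, no section says what the patient takes between the 28th tablet and the TEE. These patients have a documented atrial thrombus and were on no oral anticoagulant at baseline (exclusion 13). A gap in study drug just before the scan that measures the primary endpoint is undesirable both for the patient and for a claim about resolution on edoxaban.

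For an early visit, a patient who does everything asked can be labelled as less than fully compliant only because the appointment fell early in a permitted window. At stake are a dosing instruction, which belongs in the protocol, and the correctness of the reported compliance classes.

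**Working it through.** **Inputs.** Visit window 28 ± 3 = days 25 to 31 (flow-chart); one tablet daily for 28 days (7.2); cuts of 28 and 21 tablets (9.3, 14.9); half-life 10 to 14 hours (2.3).

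**The plan's own figures.** 1.00 × 28 = 28 and 0.75 × 28 = 21. Both cuts are reproduced, so the denominator is the nominal 28-day course.

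**Gap before a late TEE if 7.2 is followed literally.** The protocol does not say whether the first dose is on day 0 or day 1.

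- First dose day 0: last dose day 27. Dose-free days before a visit on day 29, 30 or 31 are 1, 2 or 3.
- First dose day 1: last dose day 28. Dose-free days are 0, 1 or 2.

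For a day-31 TEE the last dose is then about 72 to 96 hours old, assuming the same clock time. With the longest stated half-life, 72/14 = 5.1 half-lives, which leaves about 3% of the drug.

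**Compliance by visit day.** Take one dose due per elapsed day (d doses by day d). The class a full adherer receives depends on d/28. A true 75% needs 0.75 × d tablets, rounded up. Rows 29 to 31 assume that dosing runs to the visit.

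| Visit day | Due | Full adherence / 28 | Class given | Tablets for a true 75% | Wrongly classed by the 21-tablet cut |
|---|---|---|---|---|---|
| 25 | 25 | 89.3% | adequate | 19 | 19 (76.0%), 20 (80.0%): non adequate |
| 26 | 26 | 92.9% | adequate | 20 | 20 (76.9%): non adequate |
| 27 | 27 | 96.4% | adequate | 21 | none |
| 28 | 28 | 100% | complete | 21 | none |
| 29 | 29 | 103.6% | complete | 22 | 21 (72.4%): adequate |
| 30 | 30 | 107.1% | complete | 23 | 21 (70.0%), 22 (73.3%): adequate |
| 31 | 31 | 110.7% | complete | 24 | 21 (67.7%), 22 (71.0%), 23 (74.2%): adequate |

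On late visits the 28-tablet cut is too lenient as well: 28/29 = 96.6%, 28/30 = 93.3% and 28/31 = 90.3% all count as *complete*. If dosing stops at 28 tablets instead, 28 is the number due and there is no late-visit scoring error. A given patient can have the late gap or the late scoring error, not both.

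**Sensitivity to the dosing convention.** If the day-0 and visit-day doses both count, d + 1 doses are due. Full adherence is then 26/28 = 92.9% on day 25, 27/28 = 96.4% on day 26 and 28/28 = 100% on day 27, so the *complete* class is out of reach only on days 25 and 26. The 21-tablet cut then errs early only for 20 of 26 (76.9%) on day 25. If the first dose is on day 1 and the visit-day dose does not count, 24 doses are due on day 25 and full adherence scores 24/28 = 85.7%.

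**The case against.** The best reply is that the dosing sections fit together. Sections 7 and 7.2 give a nominal course. Section 7.1 is a supply instruction under packaging and sets no rival duration. A top class that allows more than 28 tablets makes most sense if dosing past day 28 was foreseen. This largely stands. A reader might infer that 7.1 and 7.2 flatly contradict each other, or that patients will be left without anticoagulation before the scan. The text supports neither: 7.1 can be reconciled with a nominal course, the gap arises only if 7.2 is followed to the letter, and other anticoagulation is not barred. What remains is that 7.2 is the dosing instruction, and it says 28 days without covering a permitted later visit.

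It can also be said that a nominal-course denominator is a common convention and that no analysis is tied to these three classes. The second part is correct and limits the size of the point. The first does not rescue labels that the protocol's own visit window makes wrong.

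A reader might go further and infer that the Per Protocol set is distorted. With 28 as denominator, 0.80 × 28 = 22.4, so 23 tablets would be needed, and a patient with 20 to 22 of 25 doses due on day 25 (80 to 88%) would be left out. That denominator is an assumption: 14.4 does not state one, and a statistical analysis plan may supply it. It should not be called an error.

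**Conclusion.** The point holds as a minor one, in two parts.

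1. Section 7.2 does not cover visits on days 29 to 31. Taken literally it gives up to 3 dose-free days before the primary TEE (up to 2 if dosing starts on day 1). Dosing to the visit is the likelier intention and should be written down.
2. The fixed counts in 9.3 and 14.9 do not follow the visit day. Under one dose per elapsed day, the 28-tablet cut understates adherence on days 25 to 27 and the 21-tablet cut on days 25 and 26 only. If the day-0 and visit-day doses both count, the 28-tablet error is confined to days 25 and 26. If dosing runs to the visit, both cuts overstate adherence on days 29 to 31.

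The consequence for efficacy is slight. Section 14.7.1 says "The primary analysis will be performed both on the FAS and the PP sets", and the FAS has no compliance cut, so its result is untouched. The sample size of 25 and the stated 39-79% interval do not depend on any of this. No effect on the Per Protocol result is claimed.

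**What to change.** - **Section 7.2 (with Section 7 and the synopsis aligned).** State that edoxaban continues once daily until the week-4 TEE. Say whether the first dose is on day 0 or day 1 and whether a dose is due on the visit day.
- **Section 7.1.** Dispense enough for a day-31 visit: 31 tablets, or 32 if the day-0 and visit-day doses both count.
- **Sections 9.3 and 14.9.** Define compliance as tablets taken divided by doses due from first dose to the visit. Put the 100% and 75% cuts on that ratio and drop the counts of 28 and 21.
- **Section 14.4.** Use the same ratio for the 80% cut, so that its denominator is stated. The difference between 75% for *adequate* and 80% for Per Protocol is a separate matter that this does not settle.

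The cost is 3 to 4 extra tablets per patient (31 − 28 and 32 − 28) and a denominator that differs by patient. Visits, endpoint and sample size stay as they are. Exposure will still range over 25 to 31 days, which is acceptable as a scheduling tolerance.
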